3.1.1 Treatment Administration

Every subject allocated in the AT-III (Human) treatment group will receive, immediately after anesthesia induction, a single dose of AT-III (Human) sufficient to achieve an absolute increase (Δ) of 20% above pretreatment AT levels according to the following formula, where IU means international unit:

$$AT-III \text{ dose (IU) required} = \frac{(20) \times (\text{subject weight in kg})}{1.4}$$

The only variable in the equation is the subject's body weight. For calculating AT-III (Human) dose, subject's weight obtained during the Screening visit will be used. Since the original protocol required that patients have an AT level < 80% for eligibility, the original equation differed (i.e., AT-III dose (IU) required = (100 - actual AT level in subject) x (subject weight in kg) / 1.4), as the aim was to raise AT level to 100%; given the near impossibility to recruit anyone with a subnormal AT level from the general pre-surgical population the above formula was instituted through protocol Amendment 3 (Version 4.0), 2 April 2015.

AT-III (Human) or Placebo (0.9% NaCl) will be prepared according to the volume calculated by unblinded pharmacist or designee.

AT-III (Human) will not be administered postoperatively unless the investigator decides otherwise for clinical reasons (if this is the case, the subject will be excluded from the per-protocol population for efficacy analysis and also from the mITT population as a sensitivity analysis of the primary efficacy variable).

3.2 Study Objectives

3.2.1 Primary Efficacy Objective

The primary objective of this clinical study is to compare the percentage of subjects with any component of a major morbidity composite between 2 groups of subjects randomly allocated to receive preoperative supplementation of AT-III (Human) or Placebo.

3.2.2 Secondary Efficacy Objectives

The secondary objectives of this clinical study are the following:

1. To compare postoperative AT levels at the ICU admission between the AT-III (Human) treatment group and Placebo control group
2. To compare the following postoperative outcomes between the AT-III (Human) treatment group and Placebo control group:
 - Postoperative chest-drain blood loss in the first 12 and 24 hours after surgery
 - Transfusion requirements
 - Need for surgical reexploration
 - Low cardiac output syndrome
 - Myocardial infarction (MI)
 - Stroke
 - Acute kidney injury (AKI)
 - Arterial or venous thromboembolic events
 - Infections
 - Prolonged mechanical ventilation (>24 hours)
 - All-cause postoperative mortality
 - ICU stay duration
 - Prolonged ICU stay (>6 days)
 - Length of hospital stay

3.2.3 Safety Objectives

Safety objectives include evaluation of AT-III (Human) for clinical safety including adverse events (AEs), risks for bleeding, clinical laboratory testing, physical exam, and vital signs.

4 Study Variables

4.2 Efficacy Variables

4.2.1 Primary Efficacy Variable

Percentage of subjects with any component of a **major morbidity composite** defined as a composite of any one or more of the following events (up to Day 30±4 days):

- a. Postoperative **mortality** (defined as all deaths occurring within 30 days of the operation or occurring during the primary hospitalization).
- b. **Stroke** (defined as a clinical diagnosis of focal or global neurological deficit of abrupt onset caused by a disturbance in cerebral blood supply).
- c. **Acute kidney injury (AKI)** (defined as an increase of serum creatinine levels to >2.0 mg/dL and twice the baseline level or a new requirement for dialysis postoperatively).
- d. **Surgical reexploration** (defined as having to return to the operating room because of bleeding, tamponade, graft occlusion or any other cardiac reason).
- e. **Arterial or venous thromboembolic event** (consisting of perioperative MI, mesenteric infarction, peripheral thromboembolism, acute coronary graft thrombosis, intracardiac thrombosis, deep vein thrombosis [DVT], and pulmonary embolism).
- f. **Prolonged mechanical ventilation** (defined as mechanical ventilation >24 hours).
- g. **Infection** (defined as presence of deep sternal-wound infection and/or bloodstream infections).

4.2.2 Secondary Efficacy Variables

1. AT activity (levels) determinations:

To maintain the study blind, No unblinded AT concentration results will be provided to study sites or blinded Grifols personnel until after closure of the study database.

- a. AT activity levels will be measured for both AT-III (Human) treatment and Placebo control groups at the following time points:
 - Prescreening visit (local lab)*
 - Screening visit (local lab)*§
 - Screening visit
 - Preoperatively
 - Immediately before study drug administration
 - Immediately after study drug administration
 - Postoperatively at ICU admission
 - Postoperatively Day 1
 - Postoperatively Day 2
 - Postoperatively Day 3
 - Postoperatively Day 5
 - ICU discharge
 - 1-month follow-up visit

- * Only applicable for subjects undergoing isolated CABG or single valve repair/replacements (will be needed for eligibility only if subject not receiving preoperative heparin [see entry criteria]).
- § This AT (local lab) determination will not be required if the Prescreening visit is conducted.
- b. Percentage of subjects with AT levels of 58% or higher at the ICU admission will be calculated for both treatment groups and compared.

2. **Chest-drain blood loss** (mL) in the first 12 and 24 hours of chest closure is defined as the amount of blood collected in the cardiotomy reservoir from chest closure through the following 12 and 24 hours measured.
3. **Transfusion requirements** will be measured as the number of units of Fresh frozen plasma (FFP), red blood cells (RBCs), platelets (PLTs), cryoprecipitate, fibrinogen concentrate, prothrombin complex concentrates (PCCs), plasma, and whole blood from the day of ICU admission and throughout the follow-up period.

A specific perioperative transfusion algorithm will be applied:

Standardized Transfusion Algorithm

Red blood cells (RBC):

Administration of RBCs should be performed one unit at a time after which the hemoglobin (Hb) levels should be reanalyzed to check the suitability for the next unit.

- Hb <6.0 g/dL (≤ 3.72 mmol/L [millimoles/liter]): Transfusion is mandatory
- Hb = 6.0-8.0 g/dL (3.72-4.96 mmol/L): Transfusion is optional
- Hb = (8.0-10.0 g/dL). Transfusion is acceptable only if clinically justified*
- Hb >10.0 g/dL: Transfusion is not permitted.

* One or more of the following clinical justifications must be provided:

- Central venous saturation (Swan Ganz / Central Venous Pressure (CVP) <60% with an arterial oxygen saturation of at least 90%.
- Cardiac Index <2.0 unresponsive to inotropic or mechanical support (catecholamine, intra-aortic balloon pump [IABP], etc.).
- Signs / symptoms of organ ischemia, such as: change in ST-segment or left ventricular wall motion abnormalities (LV).

Coagulation products:

Only if subject is bleeding 4 mL/kg/hour or more over at least 30 minutes or 1.5 mL/kg/hour or more over 2 consecutive hours.

- FFP (10-15 mL/kg) / PCC: If subject is actively bleeding and presents an international normalized ratio (INR) ≥ 1.5 .
- PLT: 1 apheresis unit or 4-6 pooled units if the PLT count is <100,000/ μ L.
- Cryoprecipitate / Fibrinogen concentrates: Administration of 8-10 units of cryoprecipitate or 2 grams of fibrinogen concentrate if the concentration of fibrinogen ≤ 1.5 g/L.

Shed blood collected during surgery can be retransfused according to institutional practice. Retransfusion of chest-drain collected blood is not permitted.

4. Percentage of subjects needing **surgical reexploration** defined as having to return to the operating room because of bleeding, tamponade, graft occlusion or any other cardiac reason will be considered from chest closure to the end of the follow-up period.
5. Percentage of subjects with **low cardiac syndrome** defined as the need for major inotropic support or intra-aortic balloon pump will be considered from the day of ICU admission and throughout the follow-up period.
6. Percentage of subjects with postoperative **MI** defined through enzymatic criteria plus new Q-waves at the electrocardiogram (ECG) will be considered from the day of ICU admission and throughout the follow-up period.

A perioperative MI is diagnosed by the following criteria:

- (0-24 hours postoperation):

The creatine phosphokinase-MB isoenzyme CK-MB (or creatine phosphokinase [CK] if MB not available) must be greater than or equal to 5 times the upper limit of normal, with or without new Q waves present in two or more contiguous ECG leads. No symptoms required.

- (>24 hours postoperation): Documented by at least one of the following criteria:

- a. Evolutionary ST-segment elevations
- b. Development of new Q-waves in two or more contiguous ECG leads
- c. New or presumably new left bundle branch block (LBBB) pattern on the ECG
- d. CK-MB (or CK if MB not available) ≥ 3 times the upper limit of normal

7. Percentage of subjects with postoperative **stroke** defined as a clinical diagnosis of focal or global neurological deficit of abrupt onset caused by a disturbance in cerebral blood supply will be considered from the day of ICU admission and throughout the follow-up period.
8. Percentage of subjects with **AKI** defined as an increase of serum creatinine levels to >2.0 mg/dL and twice the baseline levels or new requirement for dialysis postoperatively, will be considered from the day of ICU admission and throughout the follow-up period. A new requirement for postoperative dialysis may include hemodialysis, peritoneal dialysis, and any form of ultrafiltration.
9. Percentage of subjects with **arterial or venous thromboembolic events** defined as perioperative MI, stroke, mesenteric infarction, peripheral thromboembolism, acute

coronary graft thrombosis, intracardiac thrombosis, DVT, and pulmonary embolism, will be considered from the day of ICU admission and throughout the follow-up period.

10. Percentage of subjects with **infections** defined as presence of deep sternal-wound infections involving muscle, bone or mediastinum or bloodstream infections from the day of ICU admission and throughout the follow-up period.

The diagnosis of infection must have at least one of the following conditions:

- a. Wound opened with excision of tissue or reexploration of the mediastinum
- b. Positive culture
- c. Treatment with antibiotics

11. Percentage of subjects with **prolonged mechanical ventilation** defined as the need for mechanical ventilation >24 hours from the day of ICU admission and throughout the follow-up period. Duration of mechanical ventilation is cumulative, i.e., summed if reintubation medically necessary during hospitalization.

12. Percentage of subjects with **all-cause postoperative mortality** defined as death during the same hospitalization as surgery or after discharge and throughout the follow-up period.

13. **ICU stay** duration (days) defined as the ICU discharge date minus the ICU admission date plus 1 day. If the discharge date is beyond the follow-up period and only ' >1 month ' is recorded then it will be reported as is in data listing; and date of last follow-up minus the ICU admission date plus 1 day or 34 days, whichever is longer, will be assigned for the statistical summary and analysis.

14. Percentage of subjects with **prolonged ICU stay** defined as >6 days will be considered from ICU admission.

15. **Length of hospital stay** (days) defined as the hospital discharge date minus the surgery date plus 1 day. If the discharge date is beyond the follow-up period and only ' >1 month ' is recorded then it will be reported as is in data listing; and date of last follow-up minus the surgery date plus 1 day or 34 days, whichever is longer, will be assigned for the statistical summary and analysis.

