All AT measurements will be performed on a central venous catheter blood sample, if the central venous catheter is already in place, through a calibration curve prepared by serial dilution of the human normal plasma pool and expressed as a percentage of activity. If a central venous catheter is not already in place, peripheral blood sample will be used for measuring AT levels.

3. Chest-drain blood loss (mL) will be measured within the first 12 and 24 hours of chest closure.

Chest-drain blood loss in the first 12 and 24 hours is defined as the amount of blood collected in the cardiotomy reservoir from chest closure through the following 12 and 24 hours measured.

4. **Transfusion requirements** will be measured as the number of units of Fresh frozen plasma (FFP), red blood cells (RBCs), platelets (PLTs), cryoprecipitate/fibrinogen, prothrombin complex concentrates (PCCs), from the day of ICU admission and throughout the follow-up period.

A specific perioperative transfusion algorithm will be applied:

Standardized Transfusion Algorithm

Red blood cells:

Administration of RBCs should be performed one unit at a time after which the hemoglobin (Hb) levels should be reanalyzed to check the suitability for the next unit.

- Hb <6.0 g/dL (≤ 3.72 mmol/L [millimoles/liter]): Transfusion is mandatory
- Hb = 6.0-8.0 g/dL (3.72-4.96 mmol/L): Transfusion is optional
- Hb = (8.0-10.0 g/dL). Transfusion is acceptable only if clinically justified*
- Hb >10.0 g/dL: Transfusion is not permitted.

* One or more of the following clinical justifications must be provided:

- Central venous saturation (Swan Ganz / Central Venous Pressure (CVP) <60% with an arterial oxygen saturation of at least 90%.
- Cardiac Index (CI) <2.0 unresponsive to inotropic or mechanical support (catecholamine, intra-aortic balloon pump [IABP], etc.).
- Signs / symptoms of organ ischemia, such as: change in ST-segment or left ventricular wall motion abnormalities (LV).

Coagulation products:

Only if subject is bleeding 4 mL/kg/hour or more over at least 30 minutes or 1.5 mL/kg/hour or more over 2 consecutive hours.

- Fresh frozen plasma (10-15 mL/kg) / Prothrombin complex concentrates: If subject is actively bleeding and presents an INR ≥ 1.5 .
- Platelets: 1 apheresis unit or 4-6 pooled units if the PLT count is <100,000/ μ L.

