5.1.3.2 Secondary Efficacy Analyses

Postoperative AT levels at the ICU admission will be summarized by treatment group. The analysis of covariance (ANCOVA) will be used to compare the treatment difference. ANCOVA model will include the AT level as dependent variable, treatment as fixed effect and baseline AT level as covariate. The similar approach will also be used to analyze the AT levels in other time points.

Postoperative chest-drain blood loss in the first 12 and 24 hours after surgery will be summarized by treatment group and will be analyzed using group t-test.

For transfusion requirements, Number of units of RBC, Number of units of FFP, and Number of units of platelets will be summarized by treatment group and analyzed using group t-test.

The number and percentage of subjects with each following procedure or morbidity will be separately summarized by treatment group and will be analyzed using Chi-square test (or Fisher Exact test as appropriate)

- Need for surgical reexploration
- Low cardiac output syndrome
- Myocardial infarction
- Stroke
- Acute kidney injury
- Arterial or venous thromboembolic events
- Infections
- Prolonged mechanical ventilation (>24 hours)

- All-cause postoperative mortality
- Prolonged ICU stay (>6 days)

Duration of ICU stay and the length of hospital stay will be summarized by treatment group. Non-parametric will be used to compare the treatment differences and Hodges-Lehmann estimation will be provided.

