10.2 Secondary Efficacy Analyses

All secondary efficacy analyses will be performed by treatment group based on the mITT population. No multiplicity adjustment will be performed.

All AT activity level data will be presented in listings. Postoperative AT levels at the ICU admission will be summarized. The analysis of covariance (ANCOVA) will be used to compare the treatment difference. ANCOVA model will include the AT level as the dependent variable, treatment as the fixed effect and baseline AT level (last available AT level from central laboratory before study drug administration) as the covariate. The same analyses will also be conducted for AT levels at other time points.

The number and percentage of subjects with AT levels of 58% or higher at the ICU admission will be summarized and compared with Chi-square test (or Fisher Exact test as appropriate).

Postoperative chest-drain blood loss in the first 12 and 24 hours after surgery will be listed, and will be summarized and analyzed using group t-test.

All data about transfusion requirements will be listed and summarized for the mITT population. Each blood product (e.g., RBCs, FFP, PLTs, cryoprecipitate, fibrinogen concentrate, PCCs, plasma, and whole blood) will be summarized separately and analyzed using group t-test. Cell saver blood use will also be analyzed. If the assumptions for parametric test are not met, the non-parametric test (Wilcoxon signed rank test) will be used. Shapiro-Wilk test will be used to test the normality.

Duration of ICU stay and the length of hospital stay will be listed and summarized. The non-parametric Wilcoxon rank sum test will be used to compare the treatment difference, and the Hodges-Lehmann estimate and 95% confidence interval (CI) will be provided.

Number and percentage of subjects with each following procedure or morbidity will be separately summarized and analyzed using Chi-square test (or Fisher Exact test as appropriate). Separate listings will be provided, except all-cause postoperative mortality which will be included in the listing of deaths. A separate eCRF page for Stroke was added while the study was underway, including questions of 'Had a stroke?', 'stroke number', 'stroke date/time', and 'stroke type'. For subjects without the Stroke page, all AEs will be evaluated for stroke events by the medical review.

- Need for surgical reexploration
- Low cardiac output syndrome
- Myocardial infarction (MI)
- Stroke
- Acute kidney injury (AKI)

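### Platelet transfusion is analysed as a raw number of units, although one platelet treatment under the trial's own algorithm can be 1 apheresis unit or 4-6 pooled units

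*SAP*

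**What the plan says.** SAP 4.2.2, item 3, defines transfusion requirements by product: each "will be measured as the number of units of Fresh frozen plasma (FFP), red blood cells (RBCs), platelets (PLTs" and so on, from the day of ICU admission to the end of follow-up. Under SAP 10.2 each blood product "will be summarized separately and analyzed using group t-test". If the parametric assumptions fail on a Shapiro-Wilk check, a Wilcoxon test replaces the t-test. Protocol 5.1.3.2 has the same measure: "Number of units of platelets will be summarized by treatment group and analyzed using group t-test".

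The standardized transfusion algorithm in SAP 4.2.2 sets the platelet treatment for a bleeding subject with a count below 100,000/μL as "1 apheresis unit or 4-6 pooled units". Protocol 3.5.1 has the same line: "Platelets: 1 apheresis unit or 4-6 pooled units if the PLT count is" below that threshold. For low fibrinogen the algorithm allows "8-10 units of cryoprecipitate or 2 grams of fibrinogen concentrate".

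Neither document defines a platelet unit for analysis, converts pooled to apheresis units, reports the two forms separately, tells sites which to use, or puts site in the transfusion analysis. The synopsis plans 35 centers. MI history is the only stratification factor named.

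**The concern.** The algorithm gives two ways of delivering one platelet treatment, and the outcome counts them on scales that differ by a factor of 4 to 6. Two subjects with the same need and the same treatment could score 1 and 5 because different products were on the shelf. A mean of 1.8 platelet units then cannot be read as an amount of need without knowing the product mix.

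Bleeding is the harm that the background sections of both documents single out for AT supplementation, and platelet use is one of its quantitative readouts. Noise in that readout makes a real difference harder to see.

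A smaller gap sits beside it. SAP 4.2.2 counts fibrinogen concentrate in units, while the algorithm expresses it in grams.

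**Working it through.** **The plan's own figures.** The documents give no expected platelet use, SD or power for transfusion. The only relevant figure is 192 subjects per arm (SAP 5.3). It reproduces for the primary endpoint with two-sided alpha 0.15, 70% power and unpooled variance: (1.440 + 0.524)² × (0.22×0.78 + 0.143×0.857) / 0.077² = 191.4, so 192. It is used below only as the group size.

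**Inputs**
- From the documents: one platelet treatment is 1 apheresis unit or m = 4 to 6 pooled units; n = 192 per arm.
- Assumed: platelet treatments per subject N are Poisson with mean L = 0.6 in one arm and 0.78 in the other (+30%); a share q = 0.5 of subjects receive pooled product; m = 5; two-sided 5% level.

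**1. Mean and variance of raw units.** Let K be units per treatment (1 or m).
- E[K] = 0.5×1 + 0.5×5 = 3; E[K²] = 0.5×1 + 0.5×25 = 13; Var(K) = 13 − 9 = 4.
- Mean of KN = 3 × 0.6 = 1.8.
- Var(KN) = E[K²]·Var(N) + L²·Var(K) = 13×0.6 + 0.36×4 = 9.24, so SD = 3.04.
- Efficiency relative to counting treatments = (1.8²/9.24) / (0.6²/0.6) = 0.351/0.6 = 0.58.

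**2. Power of the t-test (normal approximation)**
- Treatments: difference 0.18; SE = √((0.6 + 0.78)/192) = 0.0848; z = 2.12; power = Φ(2.12 − 1.96) = 56%.
- Raw units: difference 3 × 0.18 = 0.54; variance in the higher arm = 13×0.78 + 0.6084×4 = 12.57; SE = √((9.24 + 12.57)/192) = 0.337; z = 1.60; power = Φ(1.60 − 1.96) = 36%.

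Simulation of the same case gives about 55% and 36%.

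**3. Power under the non-parametric fallback.** In simulated data of this shape, Shapiro-Wilk rejected normality in 200 of 200 data sets, so the fallback would apply. SAP 10.2 names the signed rank test, which is for paired data; it is read here as the two-sample rank-sum test. Simulated power falls from about 52% (treatments) to 44% (raw units). A repeat with 20,000 simulated trials gave 53% and 45%, and 57% and 36% for the t-test, so the figures are good to a point or two. With a mean of 0.3 treatments the rank test hardly changes (30% to 29%). With a mean of 1.0 it falls from 76% to 58%.

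**4. A different set of assumptions.** Suppose 30% of placebo subjects receive platelets, with 1.5 treatments each on average and a 30% relative reduction on study drug. The pooled share runs from 25% to 75% and m from 4 to 6. T-test power falls from 43% (treatments) to between 23% and 37% (raw units).

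**5. Can product mix imitate a drug effect?** Take equal need in both arms, with 55% pooled in one and 45% in the other. The SD of the chance difference in share is √(2×0.25/192) = 0.051, so this is about a 2-SD imbalance.
- Means: 0.6 × (1 + 0.55×4) = 1.92 and 0.6 × (1 + 0.45×4) = 1.68; difference 0.24.
- SE = √(2×9.24/192) = 0.31; z = 0.24/0.31 = 0.77; p = 0.44.
- Simulated false-positive rates with no drug effect: 4.9% (t-test) and 5.1% (rank-sum) at a nominal 5%.

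**6. When the loss is zero.** If q = 0 or q = 1, then Var(K) = 0, E[K²] = E[K]², and the efficiency in step 1 is exactly 1.

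**The case against.** The strongest reply is that the consequence is small and conditional.
- The t-test figures describe an analysis that the SAP would probably abandon, since such data fail a normality check. Under a rank test, subjects with no platelets keep the same rank whatever the local product, and the loss is much smaller. This stands, and it is why both sets of figures are given. The rank test does not remove the problem, because ranks among transfused subjects still mix the two scales.
- Use of both products across sites is an inference. The documents leave the choice open and give no data on practice. The eCRF is not part of the documents and may count a pool as one unit or record product type. This stands too; if so, the SAP need only say it.
- The algorithm says that either product may be given, not that the two are equal. Treating them as one treatment each is the natural reading, since both answer the same trigger, but it is a reading.
- Bleeding is also covered by chest-drain loss at 12 and 24 hours, RBC units, hematocrit, treatment-emergent bleeding events and reexploration. This is one component of a secondary endpoint in a phase 2b trial without multiplicity adjustment. That limits its weight.

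A reader might also infer that separate analysis of FFP and PCC, or of cryoprecipitate and fibrinogen concentrate, is the same defect. It is not. Those products are tested on separate lines, so unlike units are not added together. Merging them or adding a combined endpoint is a matter of preference.

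**Conclusion.** The point holds for platelets. As written, the rule can score one treatment as 1 or as 4-6, with no conversion anywhere in the plan. The cost is added noise and a mean that cannot be read as need. In the central assumed case, power falls by about 19 points with the t-test (55% to 36%) and 8 points with a two-sample rank test (52% to 44%). These sizes rest on assumed platelet use, pooled share, pool size and effect.

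Two stronger readings are tempting. One is that about 42% of the information is lost (1 − 0.58). That holds only for the t-test in the central case. The other is that an imbalance in pooled-product sites could pass for a drug effect. The documents do not support this: allocation is randomized and blinded, product-mix variance is already in the standard error, and a 2-SD imbalance gives only z = 0.77.

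**What to change.** Before unblinding, define the platelet variable in SAP 4.2.2 and 10.2 as apheresis-equivalent treatments: 1 apheresis unit counts as 1, and pooled units are divided by 5, with 4 and 6 as sensitivity analyses. Add the proportion of subjects who receive any platelets, which does not depend on the product. Keep raw units in the listings. If the eCRF already records a pool as one unit, state that instead. As a clarification, give grams as the unit for fibrinogen concentrate.

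The cost is a few lines of SAP text and one derivation. If product type was not recorded, a query to sites is needed. The divisor is an analysis convention, taken from the middle of the algorithm's 4-6 range and covered by the sensitivity analyses; it changes nothing in how subjects are transfused.
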